9.3 Vital Signs

The analyses described below will be conducted for the following vital signs assessments respectively:

- Systolic blood pressure in supine position (mmHg);
- Systolic blood pressure in standing position (mmHg);
- Diastolic blood pressure in supine position (mmHg);
- Diastolic blood pressure in standing position (mmHg);
- Pulse rate in supine position (bpm);
- Pulse rate in standing position (bpm);

- Weight (kg);
- An investigator assessment of both, systolic and diastolic blood pressure in supine
 position, systolic and diastolic blood pressure in standing position, pulse rate in supine
 position and pulse rate in standing position classified as Normal / Abnormal, Not
 Clinically Significant / Abnormal, Clinically Significant.

In accordance with the Baseline value definitions for Part 1 and Part 2 in Section 0. For Part 1, the absolute change from Baseline at post-Baseline analysis visits (as defined in) will be derived as follows:

The following will be summarized by treatment group and overall for Parts 1 and 2 of the study separately:

- Observed values and change from Baseline at each analysis visit (as defined in and) for each vital sign parameter using default summary statistics for continuous variables.
- The worst post-Baseline investigator assessment will be summarized for the blood pressure (both supine and standing position together), and pulse rate (both supine or standing position together) by providing number and percentage of subjects within each assessment category.

A listing of all vital signs data including derived change from Baseline will be provided for Parts 1 and 2 of the study separately, using the Safety Analysis Set, Part 1 and Safety Analysis Set, Part 2, respectively.

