K0706 is a BCR-ABL tyrosine kinase inhibitor with limited off-target effects. Based on its mechanism of action and the results of the pre-clinical toxicology studies, the anticipated potential toxicities in humans with K0706 include K0706 is a teratogen, as are other BCR-ABL tyrosine kinase inhibitors, in view of the role of ABL signaling in embryo-fetal development. Otherwise, non-clinical toxicology studies with K0706 demonstrate a safety profile that supports administration to human subjects. In healthy controls, K0706 has been studied Potentially-related TEAEs were mild and typically caused In Parkinson's subjects, K0706 has been studied up to . TEAEs were typically and typically across subjects. is a common TEAE with other ABL inhibitors and is typically managed with stopping the treatment and often does not recur with restarting of the medication). . In the Ph+ CML study population enrolled in , in the emerging clinical data, the most commonly observed TEAEs included the following:

Additionally, certain class effects are known with the clinical use of BCR-ABL tyrosine kinase inhibitors such as Imatinib mesylate, Dasatinib, Nilotinib, and Ponatinib in the treatment of Philadelphia-positive leukemia. While some of the observed AEs are common between the BCRABL tyrosine kinase inhibitors and contribute as a class effect, specific adverse reactions are associated with the structure of the BCRABL tyrosine kinase inhibitors and are unique for the particular TKI (e.g.: Thromboembolic episodes in patients treated with Ponatinib). Since K0706 is being developed as a tyrosine kinase inhibitor for the treatment of Philadelphia-positive leukemia, AEs commonly observed with the approved BCRABL tyrosine kinase inhibitors class of drugs may be observed with the clinical use of K0706. The following AEs have been reported

during clinical studies and clinical use of BCR-ABL TKIs such as imatinib, dasatinib, nilotinib, ponatinib, and bosutinib:

- Fluid retention: It is advised to monitor subjects for the development of signs and symptoms of fluid retention
- Myelosuppression: It is advised to monitor complete blood counts regularly
- Cardiac arrhythmias: Subjects should be advised to report signs and symptoms of slow or rapid heart rate.
- Hepatic impairment: Caution is recommended in subjects with hepatic impairment
- Heart failure: Subjects should be monitored for signs or symptoms consistent with cardiac dysfunction and should be treated appropriately

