8.1.1 Vital Signs Measurements

Blood pressure and pulse will be measured at each clinic visit throughout study participation. Measurements will be made with the subject in a supine position for at least 5 minutes, followed by standing after 3 minutes. Weight will also be measured at each visit. Results will be evaluated against pre-specified criteria for clinically significant change.

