9.2 Laboratory Evaluations

Data for the following hematology, serum chemistry, urinalysis, serology, lipid profile and coagulation analytes received from central laboratory and recorded in the eCRF are to be measured at the scheduled visits indicated in the study flowchart (Table 5).

[figure not shown]
Table 5: Laboratory Tests

Hematology Test (SI unit)	Serum Chemistry Test (SI unit)	Urinalysis (dipstick)
Hemoglobin (g/L) Hematocrit (%) WBC Count (10 ⁹ /L) Differential WBC (10 ⁹ /L and %) Neutrophils Lymphocytes Eosinophils Basophils Monocytes Platelet count (10 ⁹ /L)	Sodium (mmol/L) Potassium (mmol/L) Chloride (mmol/L) CO ₂ (mmol/L) Glucose (mmol/L) BUN (mmol/L) Creatinine (mmol/L) Calcium (mmol/L) ALT (U/L) AST (U/L) Total bilirubin (mmol/L) Total protein (g/L) Amylase (U/L) Lipase (U/L) Lipase (U/L)	pH Specific Gravity Protein Glucose Ketones Bilirubin Urobilinogen Blood Nitrite Leukocyte esterase Microscopic examination of the sediment only if abnormality seen on routine tests
Serology	Lipid Profile (SI unit)	Coagulation
 HIV-1/2 Antigen/Antibody Hepatitis panel Hepatitis B Virus Surface Antigen Hepatitis C Virus Antibody 	Total Cholesterol (mmol/L) HDL (mmol/L) LDL (mmol/L) Triglycerides (mmol/L)	Prothrombin Intl. Normalized Ratio Activated Partial Thromboplastin Time

SI = International System of Units; WBC = White Blood Cell; CO₂ = Carbon Dioxide; BUN = Blood Urea Nitrogen; ALT = Alanine Aminotransferase; AST = Aspartate Aminotransferase; HIV = Human Immunodeficiency Virus; HDL = High Density Lipoprotein; LDL = Low Density Lipoprotein.

Central laboratory data will be summarized by analysis visit (as defined in and) using default descriptive summary statistics for continuous variables for Parts 1 and 2 of the study separately, by treatment group and overall. Changes from Baseline will also be summarized.

For summaries which present the worst value with respect to the reference range at the subject level, low and high are each chosen in preference to normal values. For parameters with both lower and upper limits of the reference range, subjects who have assessments within both low and high ranges will be counted within each category for worst value summary tables.

The number and percentage of subjects with worst post-baseline categorized (low, normal and high) values relative to the reference range will be summarized for Parts 1 and 2 of the study separately, by laboratory analyte, treatment group and overall.

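### The only subject-level vital-sign count in SAP 9.3 has no direction, pools positions and omits weight, so it cannot show how many subjects per arm had a marked change

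*SAP*

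**What the plan says.** Protocol 8.1.1 has blood pressure and pulse measured supine and then standing at each clinic visit. It adds "Weight will also be measured at each visit" and closes with "Results will be evaluated against pre-specified criteria for clinically significant change".

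SAP 9.3 plans three outputs:

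- Descriptive statistics, by arm, of "Observed values and change from Baseline at each analysis visit". These cover each listed parameter: systolic pressure, diastolic pressure and pulse in each position, and weight.
- One count of subjects: "The worst post-Baseline investigator assessment will be summarized for the blood pressure", with the two positions taken together, and likewise "pulse rate (both supine or standing position together) by providing number and percentage of subjects within each assessment category".
- A listing of all vital signs with the derived change.

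The rating is the investigator's. It covers blood pressure and pulse only, and the SAP describes it as "position and pulse rate in standing position classified as Normal / Abnormal, Not" clinically significant, or abnormal and clinically significant. That is three grades, none stating whether the value was high or low.

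Two neighbouring sections work differently. SAP 9.2 counts subjects by "worst post-baseline categorized (low, normal and high) values relative to the reference range", and a subject with both a low and a high value enters both categories. SAP 9.4 classifies QTcF by numeric limits for the observed value and for the change from baseline.

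**The concern.** A subject-level safety count is there to show whether some subjects in one arm had large changes that a mean would dilute. For vital signs the planned count does this poorly, for four reasons.

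- A fast and a slow pulse, or a high and a low pressure, fall in the same grade.
- Supine and standing are merged, so the count cannot point to a postural problem.
- The grade is a judgement on a value, not on a change from baseline.
- Weight is not graded, so no output states how many subjects per arm gained or lost a marked amount.

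Direction and weight matter for this drug class. Protocol 2.2.6 lists fluid retention among the class events ("It is advised to monitor subjects for the development of signs and symptoms of fluid retention"), and also arrhythmias with slow or rapid heart rate, and heart failure. Protocol 2.3.6 notes that the disease itself affects autonomic function. What is at stake is how readable the safety report is. The primary endpoint, type I error and sample size are unaffected.

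**Working it through.** The documents give no figure on this point, so there is none to reproduce. The check is a comparison of the sections, followed by an illustration whose rates and SDs are all assumed.

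**Comparison of sections**

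| Data | Subject-level count | Direction | Limit on change |
|---|---|---|---|
| Laboratory (SAP 9.2) | worst value against reference range | low / normal / high | no |
| QTcF (SAP 9.4) | maximum average value | upper limits | yes |
| Blood pressure, pulse (SAP 9.3) | worst investigator grade, positions pooled | none | none |
| Weight (SAP 9.3) | none | none | none |

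Protocol 8.1.1 names change criteria for the last two rows. Readable SAP 9.3 neither states them nor points to them.

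**Inputs.** 506 subjects (protocol synopsis) randomized 1:1:1 (protocol 5.4.2) give 506/3 = 168.7 per arm. The standard error of a difference in means is SD × √(2/168.7) = 0.109 × SD. Power figures are two-sided at 0.05. They only gauge how visible a contrast is; no test is proposed.

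**1. Opposite differences between arms.** Assume high readings in 15% on K0706 and 10% on placebo, low readings in 5% and 10%, and no subject with both. The undirected total is 15% + 5% = 20% against 10% + 10% = 20%, about 34 of 169 in each arm. With 15% high / 5% low against 5% high / 15% low, the total is again 20% v 20%, while each directional count (15% v 5%) would have about 87% power.

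**2. Would the mean-change table show it?** Treat the first pattern in step 1 as normally distributed values at one visit.

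- Upper tail, 10% to 15%: 1.282 − 1.036 = 0.25 SD.
- Lower tail, 10% to 5%: 1.645 − 1.282 = 0.36 SD.
- In standard errors: 0.245/0.109 = 2.3 and 0.363/0.109 = 3.3.

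A shift of that kind would be visible in the signed table. Similarly, a uniform 5 mmHg shift with an assumed change SD of 12 has a standard error of 12 × 0.109 = 1.31 mmHg and about 97% power.

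**3. More of both in one arm.** With 5% high and 5% low against 10% high and 10% low, the undirected counts add to 10% v 20% (power about 73%). The rating shows an excess but cannot say in which direction, and the mean can stay near zero.

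**4. Weight, a minority with marked gain.** Assume a change SD of 3 kg, so the standard error is 3 × 0.109 = 0.33 kg. For the count, assume 5% of both arms meet the criterion anyway and that it captures the extra gainers cleanly.

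| Extra subjects gaining 5 kg | Mean shift | In standard errors | Power, mean | Count | Power, count |
|---|---|---|---|---|---|
| 5% (about 8) | 0.05 × 5 = 0.25 kg | 0.8 | 12% | 5% v 10% | 41% |
| 10% (about 17) | 0.10 × 5 = 0.50 kg | 1.5 | 33% | 5% v 15% | 87% |

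The mean is a weak instrument for this pattern, and a count is clearly better.

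**The case against.** **The signed tables already do the work.** SAP 9.3 gives change from baseline by visit, separately for each position and for weight, and lists every value. A reader might infer from the 20% v 20% example that a blood-pressure effect would disappear from the report. The documents do not support that: step 2 shows that such a pattern moves the mean by 2.3 to 3.3 standard errors. Equal totals also need the extra highs to offset the missing lows exactly, and even then the clinically significant grade could differ between arms. This part of the objection stands, and it limits the point to minorities with marked change.

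**Protocol 8.1.1 promises no table.** A reader might infer that the SAP breaks a protocol commitment. Section 8.1.1 says results will be evaluated against criteria; it does not say they will be tabulated by arm. The analysis commitment is protocol 9.8.2, which asks for descriptive statistics by group and visit and a review of individual results, and SAP 9.3 supplies the statistics and the listing. This stands as to the wording. But the criteria have no visible use in the analysis, and neither 9.8.2 nor readable SAP 9.3 says what they are.

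**The criteria may exist out of sight.** Parts of the SAP are blacked out, and the table shells are a separate document. So it cannot be said that no criteria exist, only that readable 9.3 cites none.

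**Weight is analysed, and adverse events are a backstop.** A reader might infer that weight is ignored. It is not: by-visit statistics and a listing are planned. Fluid retention reported as an adverse event would be counted by preferred term. That backstop is partial. Protocol 8.1.2 and 8.1.3 require clinically significant laboratory and ECG findings to be reported as adverse events, and 8.1.1 has no such sentence for vital signs.

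**Conclusion.** The point holds as a modest gap in safety reporting. The one subject-level count for vital signs has no direction, merges positions and leaves out weight. It therefore cannot separate high from low values or show how many subjects per arm had a marked change, and readable SAP 9.3 does not use the change criteria that protocol 8.1.1 names.

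The gap concerns minorities, not uniform shifts. Under the assumed figures, 5% of an arm gaining 5 kg moves the mean by 0.8 of a standard error, and 10% by 1.5. These sizes rest on assumed event rates, an assumed SD of 3 kg and a criterion that captures the gainers cleanly, since the documents give none of these. The conclusion about the table's structure rests only on the readable text of SAP 9.3 and would change if hidden text or the table shells already contain a directional count.

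**What to change.** In SAP 9.3, add the number and percentage of subjects per arm with any post-baseline value meeting the protocol 8.1.1 criteria, defined on both the value and the change from baseline:

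- systolic pressure, diastolic pressure and pulse, each by position, with high and low shown separately;
- weight gain and weight loss, each as a percentage of baseline.

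State the criteria in SAP 9.3, or cite where they are held. The sponsor sets the thresholds before unblinding; the documents give none and none is proposed here. Keep the investigator rating unchanged as a secondary display. It should not be split into high and low, because no direction is described for it and one rating may cover a systolic and a diastolic value that lie on opposite sides.

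Cost: SAP wording, one or two more descriptive tables, and thresholds agreed in advance. No new data are needed, and the primary inference is unaffected.

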9.5 Physical Examinations

Abnormalities identified from physical examination are recorded in the eCRF as AEs and will be listed and summarized as such (See Section 6.3 [Medical History] and Section 9.1 [Adverse Events]).

In accordance with the Baseline value definitions for Part 1 and Part 2 in Section 4.1.2, for each physical examination body system, the number and percentage of subjects with abnormalities at Baseline will be summarized by treatment group and overall for Parts 1 and 2 of the study separately.

Physical examination findings (Normal / Abnormal, Not Clinically Significant / Abnormal, Clinical Significant) and details of abnormalities will be listed for each subject at each scheduled visit for Parts 1 and 2 of the study separately.

9.6 Other Safety Outcomes

A categorical summary of the composite endpoints at Baseline, at each analysis visit and the worst post-Baseline result will be provided using counts and percentages by treatment group and overall for Parts 1 and 2 of the study separately. See Section 13.5 on the composite endpoints.

9.7 Prior and Concomitant Medications

All medications will be coded using the World Health Organization (WHO) Drug Global Dictionary, (version Mar 2022 or a later version if updated during the study), Anatomical Therapeutic Chemical (ATC) classification codes.

Prior and concomitant medications are defined as follows:

- Prior medications are those medications with a stop date prior to the start of the Treatment Period.
- Concomitant medications are those with a start date on or after the start of the Treatment Period, or those with a start date before the start of the Treatment Period and either a stop date on or after the start of the Treatment Period, or are ongoing at the end of the study.
- Concomitant medications for Part 1 of the study are all concomitant medications for those subjects not participating in Part 2 of the study and those concomitant medications with start date before the date of first dose for Part 2 of the study for subjects participating in Part 2 of the study.
- Concomitant medications for Part 2 of the study are those concomitant medications with start date on or after the date of first dose for Part 2 of the study.

See Section for imputation of missing or partial dates for medication.

Prior and concomitant medications will be summarized by treatment group and overall for Parts 1 and 2 of the study separately, using the All Randomized Set, Part 1 and All Enrolled Set, Part 2, respectively, as follows:

- The number and percentage of subjects with at least one prior / concomitant medication will be presented.
- The number and percentage of subjects with at least one prior / concomitant medication within each Therapeutic Subgroup (ATC-Level 2), Chemical Subgroup (ATC-Level 4), and PT will be presented. The summary will be sorted using numerical counts by descending order of Therapeutic Subgroup, then descending order of Chemical Subgroup, then descending order of PT in the total column. Where groups or terms tie these will be sorted alphabetically.

Prior medications will be listed for the All Randomized Set, Part 1. Concomitant medications for Parts 1 and 2 of the study will be listed separately, using the All Randomized Set, Part 1 and All Enrolled Set, Part 2, respectively. In the listings the relative start and stop day of prior / concomitant medication use will be calculated relative to the first dose date of study drug in the corresponding Part period and will be presented for those subjects who received at least one dose of study drug. If the concomitant medication is "Ongoing" it will be indicated as such in the listing and the relative stop day will not be calculated. Only original dates will be presented in the listing even though the relative day may be based on an imputed date.

9.8 Extent of Exposure

Duration of exposure will be calculated in weeks as:

Duration of exposure will be summarized by treatment group and overall for Parts 1 and 2 of the study separately.

The total number and percent of doses administered per subject (and the number of subjects with doses administered since previous visit) at each scheduled site visit will be summarized using descriptive statistics by treatment group and overall.

[figure not shown]
The percentage of doses administered per subject will be calculated as the total number of doses administered divided by the total planned doses, expressed as a percentage.

Total number of doses administered per Visit will be defined as:

• For Part 1 of the study:

- For the first post-Baseline visit → (Date of the visit date of first dose for Part 1 number of doses missed since last visit)
- For subsequent visits → (Date of the visit date of the prior visit number of doses missed since last visit)
- For the last on-treatment visit \rightarrow (Date of the last dose for Part 1 date of the prior visit number of doses missed since last visit + 1)
- For Part 2 of the study:
 - For the first post-Baseline visit → (Date of the visit date of first dose for Part 2 number of doses missed since last visit)
 - For subsequent visits → (Date of the visit date of the prior visit number of doses missed since last visit)
 - For the last on-treatment visit \rightarrow (Date of the last dose for Part 2 date of the prior visit number of doses missed since last visit + 1)

Total number of doses administered in Part 1 or Part 2 will be calculated as the sum of the doses administered per Visits in Part 1 or Part 2, respectively.

A listing of overall treatment exposure data, including the first and last dates of treatment, transition dates from capsules to powder formulation, and dates of the study treatment dose reductions will be presented for Parts 1 and 2 of the study separately, using the Safety Analysis Set, Part 1 and Safety Analysis Set, Part 2, respectively.

10.0 PHARMACOKINETIC ANALYSES

Pharmacokinetic (PK) analyses will be performed on the PK Analysis Set, Part 1. There is no PK study in Part 2.

See Section 4.2.4 for the handling of plasma and CSF concentrations that are BLQ.

K0706 plasma and CSF concentration data will be summarized by dose group and assessment time-point by using descriptive statistics (such as number of subjects, mean, standard deviation, geometric mean, coefficient of variation (CV%), minimum, median, and maximum values).

PK analyses and modelling will be detailed in a separate SAP.

Statistical Analysis Plan	CONFIDENTIAL	
		Protocol Reference: CLR_18_06

12.0 CONVENTIONS

12.1 Software

The Statistical Analysis System[®] (SAS[®], version 9.4 or newer) will be used for all statistical analysis and reporting.

12.2 General rules for Statistical Reporting

In general, statistical reporting and analyses will be created separately for Part 1 and Part 2.

The default summary statistics for quantitative variables will be the number of observations (n), mean, SD, median, minimum (min) and maximum (max), for those subjects with data. In addition, geometric mean and CV% of geometric mean will be reported for PK parameters.

All summary statistics will be rounded (using the more decimal place than the raw value, except for the SD and SE values that will be presented to 2 more decimal places than the raw value, and minimum and maximum values that will be presented with the same decimal precision as the raw value. All summary statistics for PK data will be rounded (using the analysis) and presented to 3 significant figures, except for the geometric CV values that will be presented to 1 decimal place.

For qualitative variables, the number (n) and percentage (%) of subjects with non-missing data per category will be the default summary presentation, and where appropriate and present, the number of missing values as a "Missing" category. The number of subjects in the analysis population will be used as denominator for percentages calculation, unless stated otherwise in Tables, Figures and Listings (TFL) mock shell(s).

All statistical comparisons and tests will be performed at the significance level unless specifically stated otherwise.

All central laboratory test results will be provided in International System of Units (SI) and all local laboratory test results will be provided in conventional units.

For the TFL, the results will be summarized or presented in Refer to Appendix of the TLF mock shells for the SI unit corresponding to each laboratory test and the precision level in which each laboratory test is reported by the central laboratory.

Specifications for table, figures and data listing formats can be found in the TFL shells specifications for this study. Please refer to "2. General Format Guidelines" section within TFL shells for more details on presentation of results.

Protocol Reference: CLR 18 06 RATING SCALES: SCORING AND HANDLING OF MISSING DATA 13.1 MDS-UPDRS The MDS-UPDRS contains questions/ratings, which are divided into Part I (13 items), Part II (13 items), and Part III The total score of each part will be calculated as the sum of individual items' scores within the corresponding Part. In case of missing item scores, prorated scores for each part of the MDS-UPDRS will be calculated as the sum of the available individual item scores multiplied by the number of total items in the complete part of the MDS-UPDRS, and this result was divided by the number of items with actual scores. The number of permissible missing items for generating a valid prorated score is 1 missing item for Part I, 1 missing item for Part II and 3 missing items for Part III. If the number of missing item scores exceeds the number of permissible missing items, then the prorated score will not be valid and will be kept missing. If the total score for either Part II or Part III is missing, then the sum of MDS-UPDRS Parts II and III total scores will be missing. For the primary and secondary efficacy analyses, if any assessment on MDS-UPDRS is captured on or after the day of the initiation of symptomatic PD medications, it will be treated as a missing value. 13.2 CGIS , with the severity of illness scale using a range of responses The CGIS is rated on a 13.3 EQ-5D-5L The 13.4 SCOPA-AUT The SCOPA-AUT is a specific 23-item self-completed questionnaire for the assessment of

[figure not shown]
autonomic dysfunction in subjects with PD.

Statistical Analysis Plan	CONFIDENTIAL
In case of a valid SCOPA-AUT	score (i.e., with a valid re

In case of a valid SCOPA-AUT score (i.e., with a valid response on score of the questions), the SCOPA-AUT total score will be transformed to a scale from 0 to 100 points.

If the number of items with a valid response is

SCOPA-AUT total score will keep blank, i.e., a missing value.

- –
- _____
- — —
- •
- . ____

- -

Protocol Reference: CLR_18_06

Statistical Analysis Plan	CONFIDENTIAL	Protocol Reference: CLR_18_06

Statistical Analysis Plan	CONFIDENTIAL	
·		Protocol Reference: CLR_18_06

